## 6.2 Study Drug

RBT-9 (stannous protoporphyrin) is an agent that preconditions the body to combat insult and injury by eliciting an early stressor response, which subsequently boosts cytoprotective, anti-inflammatory responses that preserve functional and structural organ integrity. In addition to broad organ protection, RBT-9 possesses antiviral activity, which has been demonstrated against several enveloped viruses.

In Phase 1 clinical development conducted by Renibus, Therapeutics, Inc., RBT-9 has been shown to be safe and well tolerated. It was also shown to upregulate the cytoprotective/anti-inflammatory pathways (ie, nuclear factor erythroid 2-related factor 2 [Nrf2], interleukin-10 [IL-10]) that were identified in preclinical studies. RBT-9 is administered as a single dose via intravenous infusion over a 120-minute period. An immediate stressor response is induced, which converts to an antioxidant/anti-inflammatory state within 24 to 48 hours. The antiviral activity of RBT-9, as measured in vitro, has been observed to occur within 24 hours.

The COVID-19 pandemic has now spread to 192 countries and all 50 states in the United States. Treatments that can prevent the progression COVID-19 once a diagnosis has been made (ie, Stage I, early disease) are of critical need. If high-risk patients could be offered early treatment that prevents disease progression and preserves organ function, it would lead to a reduction in ICU admission rates, which may help “flatten the curve” of healthcare utilization.

## 6.3 Preclinical Experience

### Cytoprotective Preconditioning

RBT-9 is a metalloporphyrin, well known for its ability to inhibit the antioxidant enzyme heme oxygenase-1 (HO-1), which protects against oxidative stress, inflammation, and tissue injury. However, RBT-9 is unique among metalloporphyrins in that it is a dual regulator of HO-1. Although RBT-9 initially acts as an HO-1 inhibitor by competitively binding to this enzyme and inhibiting its activity, it also induces HO-1 synthesis [Sardana 1987]. Within 18 hours in mice and 24 to 48 hours in humans, RBT-9 elicits a cytoprotective response that is at least partially mediated by activation of Nrf2, the master transcriptional regulator of the antioxidant response, which controls HO-1 production [Johnson 2017]. The cytoprotective response induced by RBT-9 has been demonstrated in several organs including the kidney, liver, heart, brain, retina, and lung [Johnson 2017; Atef 2017; Dennery 2003; Juncos 2006; Kaizu 2003; Peng 2011; Sutherland 2011; Zager 2015; Zager 2016].

In addition to HO-1, other Nrf2-regulated genes that are upregulated in response to RBT-9 are NAD(P)H dehydrogenase quinone 1 (NQO1), thioredoxin, glutathione transferase, and ferritin [Johnson 2017]. Although ferritin is often associated with an

acute inflammatory response in pathogenic conditions, it is also known to be an anti-inflammatory protein. In particular, heavy chain ferritin has ferroxidase activity, which converts iron from the ferrous state to the ferric form, preventing production of hydroxyl radical formation. RBT-9 has been shown to specifically increase heavy chain ferritin [Johnson 2017]. Additionally, IL-10, a key anti-inflammatory cytokine, is also upregulated by RBT-9 [Zager 2015], while the proinflammatory cytokine tumor necrosis factor alpha is downregulated by RBT-9 [Sutherland 2011]. Thus, the overall protein expression profile that results from RBT-9 treatment is consistent with an antioxidant and anti-inflammatory response.

The dual mechanism of inducing an acute stress response followed by a cytoprotective response makes RBT-9 an effective “preconditioning” agent that renders organs resistant to subsequent ischemic, inflammatory, or toxin-mediated attack.

### **Organ Protection**

Preclinical studies with RBT-9 have shown significant protection in the kidney, heart, and liver [Johnson 2017, Zager 2015, Zager 2016]. Preconditioning with RBT-9 was protective against ischemia/reperfusion injury [Johnson 2017]. This protection also inhibited AKI-mediated progression to chronic kidney disease (CKD). Additionally, in the ischemia/reperfusion model of AKI, animals treated with RBT-9 were protected from cardiac injury as demonstrated by inhibition of AKI-mediated increases in troponin I [Zager 2016]. Effects similar to those found in the kidney are also observed in response to RBT-9 in animals that underwent hepatic ischemia. In these animals, RBT-9 was shown to preserve liver function and structural integrity [Zager 2015].

The effects on organ protection were found to be at least partly mediated through activation of Nrf2, as Nrf2-/- animals treated with RBT-9 were not protected from AKI induced by ischemia/reperfusion [Johnson 2018]. Together, these data indicate that the initial stress response associated with HO-1 inhibition is not the prevailing response to RBT-9 treatment. Rather, it is (at least partly) through activation of the well-known cytoprotective Nrf2 pathway that RBT-9 mediates organ protection.

### **Antiviral Activity**

Natural and synthetic porphyrins are known to have antiviral activity in several enveloped viruses, including influenza, human immunodeficiency virus, hepatitis B virus, hepatitis C virus, Dengue, Yellow Fever, Chikungunya, Zika, Mayaro, Sindbis, and Vesicular Stomatitis viruses [Assuncao-Miranda 2016; Chen-Collins 2003; Guo 2011; Hou 2010; Neris 2018; Staudinger 1996; Vzorov 2002; Wen 2009]. A recent study with Dengue virus demonstrated that RBT-9 reduces viral load in HepG2 hepatocytes and THP-1 macrophages, and similar effects were observed with both Dengue and Yellow Fever viruses in BHK-21 hamster kidney cells [Assuncao-Miranda 2016]. These effects were shown to be independent of HO-1 activity, as treatment with cobalt protoporphyrin, a known inducer of HO-1 activity, also reduced viral load. Importantly, these effects were observed without a loss of host cell viability. Further, the porphyrin ring structure played a critical role in antiviral activity, as biliverdin (a noncyclical, non-iron containing metabolite of heme) did not reduce infectivity of Dengue or Yellow Fever viruses [Assuncao-Miranda 2016]. The RBT-9-mediated decrease in viral load was associated with a reduction in viral adsorption and penetration in host cells, as well as a reduction in

the expression of nonstructural protein synthesis 1 (NSP1) and inhibition of viral protein synthesis and viral RNA replication.

In a separate study, RBT-9 was also shown to be effective at inactivating Chikungunya, Zika, Mayaro, Sindbis, and Vesicular Stomatitis viruses, as demonstrated by inhibition of viral plaque formation [Neris 2018]. Inhibition of adsorption, viral entry, and viral fusion to BHK-1 cells was also observed in response to RBT-9 [Neris 2018]. Further, RBT-9 was found to alter the integrity of the viral envelope, causing a loss of symmetry, viral particle aggregation, and reduced viral envelope content. Despite damaging the viral envelope, RBT-9 preserves viral antigenicity [Neris 2018].

Together, the published data indicate that RBT-9 has broad antiviral activity and does so at the early stages of viral infectivity. The effects of RBT-9 on NSP1 are notable as this protein plays a role early in viral infection. NSP1 is one of the first proteins produced by viruses, regulates viral replication, and is critical for blocking the innate immune response that is responsible for clearance of viral infections [Enjuanes 2016; Narayanan 2015]. In human coronavirus, NSP1 is implicated in disease pathogenesis. It has been shown to suppress the antiviral immune response by inhibiting interferon-gamma, increase viral load by facilitating viral replication, and induce cytokine storm by promoting NFkB activity [Enjuanes 2016; Narayanan 2015].

The importance of NSP1 in viral activity is highlighted by the fact that it is a target for vaccine development in SARS coronavirus. Prevention of full infection by SARS coronavirus is observed when the virus is engineered without NSP1. Importantly, the resulting NSP1 mutant virus remains detectable by the immune system, which means that inhibiting NSP1 serves to both induce viral attenuation while preserving antigenicity [Zust 2007].

Similar to the enveloped viruses discussed above, NSP1 forms part of the viral replicase transcriptase complex in SARS-CoV-2 [Li 2020]. Given the published findings on the preconditioning and antiviral activity of RBT-9 treatment, this agent may be beneficial in the early stages of COVID-19, as it has the potential to: 1) provide broad organ protection, 2) reduce viral load, and 3) prevent cytokine storm that leads to multi-organ failure.

#### 6.4 Clinical Experience

Renibus Therapeutics, Inc., has completed a Phase 1 clinical study (Study REN-003) of RBT-9 in 42 subjects (18 healthy volunteers, 12 subjects with Stage 3 CKD, and 12 subjects with Stage 4 CKD). RBT-9 was administered as a single dose at 9, 27, or 90 mg, and safety was assessed through Day 28. RBT-9 was shown to be safe and well tolerated in healthy volunteers and patients with Stage 3/4 CKD.

RBT-9 was observed to increase endogenous antioxidant activity, as demonstrated by increases in plasma HO-1, NQO1, ferritin, and p21. RBT-9 also increased levels of the anti-inflammatory cytokine IL-10.

All of the adverse events were mild in severity, except for 2 adverse events associated with photosensitivity that were considered moderate in severity. The only adverse event considered possibly related to treatment was photosensitivity, which was transient and

resolved without the need for intervention in most cases. No serious adverse events or deaths occurred in this study.

Given its broad protection of various organs through generation of cytoprotective proteins and direct antiviral effect, treatment with RBT-9 may be beneficial in the early stages of COVID-19 infection in patients at high risk of disease progression by virtue of age and/or comorbid conditions.

## 7 STUDY OBJECTIVES

The overall objective is to evaluate the efficacy, tolerability, and safety of a single dose of RBT-9 versus placebo on the progression of COVID-19 infection in non-critically ill adults who are at high risk due to age and/or comorbid conditions.

### 7.1 Primary Objectives

The primary objective is to evaluate the effect of RBT-9 versus placebo on clinical status as measured using the 8-point WHO Ordinal Clinical Scale through Day 28.

### 7.2 Secondary Objective

The secondary objectives are to evaluate the effect of RBT-9 versus placebo on the following through Day 28:

- Time to first occurrence of death from any cause or new/worsened organ dysfunction
- All-cause survival
- SpO2/FiO2 ratio
- Fever incidence
- AKI incidence
- New or worsening CHF
- Hospitalization status
- Length of hospital stay
- Oxygen-free days
- ICU status
- Days on ventilator
- Time to and duration of vasopressor or inotrope utilization
- Ventricular tachycardia or fibrillation lasting at least 30 seconds and/or associated with hemodynamic instability or pulseless electrical activity, or resuscitated cardiac arrest
- Dialysis status
- Safety parameters

### **7.3 Exploratory Objectives**

The exploratory objective in this study is to evaluate the effect of RBT-9 versus placebo on the following:

- Duration of COVID-19 symptoms

## **8 INFORMED CONSENT**

The Investigator or designee will be responsible for obtaining a signed, written informed consent form (ICF) and providing a copy to each subject, legally authorized representative, or a person with legal responsibility for the subject's health care decisions prior to the performance of any clinical activities or procedures pursuant to this protocol. Subjects who are vision impaired may have the ICF read to them and their witnessed consent documented. Only the consent form approved by the Institutional Review Board (IRB) will be used. If English is NOT the subject's primary language, the subject will be consented using an IRB-approved ICF in the requisite language. This consent will be conducted by a member of the research team who is fluent in the language and thus able to answer any scientific or procedural questions raised by a non-English speaking subject.

## **9 STUDY POPULATION**

### **9.1 Inclusion Criteria**

Eligible subjects must meet all of the following criteria:

1. Male or female,  $\geq 18$  years of age at Screening.
2. Confirmed infection with SARS-CoV-2.
3. High risk of COVID-19 disease progression, defined as:
  - a. 18-69 years of age with lymphopenia AND at least 1 risk factor (described below)
  - b. 18-69 years of age without lymphopenia AND at least 2 risk factors (described below)
  - c.  $\geq 70$  years of age with lymphopenia OR at least 1 risk factor (described below)

#### Risk Factors

- Documented history of coronary artery disease
- Heart failure (New York Heart Association Class 3 or 4)
- Documented history of stroke
- Chronic lung disease (eg, asthma or chronic obstructive pulmonary disease) requiring treatment
- Diabetes mellitus, requiring at least 1 prescription medicine for management
- Documented CKD with an estimated glomerular filtration rate  $<30$  mL/min, not on dialysis
- Obesity (Class 2 or 3; body mass index  $>34.9$  kg/m^2)
- On immunosuppressive therapy
- Oxygen saturation between 90 and 95% with or without supplemental oxygen

4. Admitted to a hospital (or controlled facility such as an emergency room, urgent care facility, temporary/modular hospital, infusion center, clinical research unit, etc; hereafter referred to as hospital) for observation and/or treatment
5. If female, must be postmenopausal, surgically sterile, or if of childbearing potential, must be practicing 2 effective methods of birth control during the study and through 30 days after completion of the study.
6. For females of childbearing potential, a urine pregnancy test must be negative at the Screening Visit.
7. If male, must be surgically sterile or willing to practice 2 effective methods of birth control during the study and through 30 days after completion of the study.
8. Must be willing and able to give informed consent and comply with all study procedures.

## **9.2 Exclusion Criteria**

Subjects will be ineligible for study participation if they meet any of the following criteria:

1. Anticipated need for ICU care and/or ventilatory support (invasive or non-invasive) within 24 hours.
2. Evidence of acute cardiac injury, as determined by the Investigator at the time of Screening. This may be based upon clinical signs and symptoms, ECG findings, or elevated troponin I.
3. Evidence of acute kidney injury not due to pre-renal azotemia or urinary tract obstruction at the time of Screening.
4. Oxygen saturation <90% on supplemental oxygen with a nasal cannula, including high-flow oxygen.
5. Requires non-invasive ventilation at the time of Screening.
6. Requires dialysis at the time of Screening.
7. Has received or is receiving anti-IL-6 therapies (eg, Tocilizumab, Sarilumab, Silituximab, etc) for the treatment of COVID-19; subjects receiving anti-IL-6 therapies for underlying medical conditions that are unrelated to COVID-19 are not excluded from eligibility.
8. Pregnant or lactating.
9. History of photosensitivity or active skin disease that, in the opinion of the Investigator, could be worsened by RBT-9.
10. Known hypersensitivity or previous anaphylaxis to RBT-9 (stannous protoporphyrin) or any tin-based product.
11. Treatment with an investigational drug or participation in an interventional trial within 30 days prior to treatment with study drug.
12. Has received COVID-19 vaccination.

13. Has received anti-SARS-CoV-2 antibody therapy.
14. Inability to comply with the requirements of the study protocol.

### **9.3 Study Design**

This is a Phase 2, randomized, placebo-controlled, multicenter study that will evaluate the efficacy, tolerability, and safety of a single dose of RBT-9 on the progression of COVID-19 infection in non-critically ill adults who are at high risk due to age and/or comorbid conditions. Subjects with documented SARS-CoV-2 infection who are at high risk for disease progression, as defined in the inclusion criteria (see [Section 9.1](#)), and require observation and/or treatment in a hospital will be screened for entry into the study. Eligible subjects will be stratified by time since COVID-19 diagnosis (<48 hours,  $\geq$ 48 hours) and randomly assigned in a 2:1 ratio to receive a single intravenous infusion of 90 mg RBT-9 or placebo (normal saline). No more than 24 hours can elapse between Screening and Dosing of RBT-9.

All subjects will be assessed through Day 56. All subjects, regardless of hospitalization status, will be assessed on Days 7, 14, 21, and 28, according to the Event Schedule (see [Section 5.1](#)). Assessments will include severity of COVID-19 measured by the 8-point WHO Ordinal Clinical Scale, physical examination, vital signs, clinical laboratory evaluations, concomitant medications, and adverse events. For subjects who have been discharged from the hospital, visits on Days 7, 14, and 21 will be conducted virtually (eg, by telephone or video contact). The Day 28 visit should be conducted in person, but may be conducted virtually, as well. Subjects will also be assessed at safety follow-up visits, which will be conducted virtually (eg, by telephone or video contact) on Days 42 and 56.

An independent data and safety monitoring board (DSMB) will actively monitor interim data to make recommendations regarding study conduct/continuation. The DSMB will meet once the first 30 subjects complete the Day 7 assessment to perform the first interim analysis of the safety data. Enrollment of 30 additional subjects will proceed if the safety profile of RBT-9 is deemed acceptable (as determined by the DSMB). Two additional DSMB interim analyses will be performed once 60 and 90 subjects complete the Day 7 evaluation. The last DSMB interim analysis will be performed once 150 subjects complete the Day 28 evaluation; sample size re-estimation will also be performed to allow a sample size increase to 252 subjects based on pre-defined conditional power rules.

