critically ill adults who are at high risk due to age and/or comorbid conditions. Subjects with documented SARS-CoV-2 infection who are at high risk for disease progression, as defined in the inclusion criteria (see [Section 9.1](#)), and require observation and/or treatment in a hospital (or controlled facility such as an emergency room, urgent care facility, temporary/modular hospital, infusion center, clinical research unit, etc; hereafter referred to as hospital) will be screened for entry into the study. Eligible subjects will be stratified by time since COVID-19 diagnosis (<48 hours,  $\geq$ 48 hours) and randomly assigned in a 2:1 ratio to receive a single intravenous infusion of 90 mg RBT-9 or placebo (normal saline). No more than 24 hours can elapse between Screening and RBT-9 Dosing.

All subjects will be assessed through Day 56. All subjects will be assessed on Days 7, 14, 21, and 28, according to the Event Schedule (see [Section 5.1](#)). Assessments will include severity of COVID-19 measured by the 8-point WHO Ordinal Clinical Scale, physical examination, vital signs, clinical laboratory evaluations, concomitant medications, and adverse events. For subjects who have been discharged from the hospital, visits on Days 7, 14, and 21 will be conducted virtually (eg, by telephone or video contact). The Day 28 visit should be conducted in person, but may be conducted virtually. Subjects will also be assessed at safety follow-up visits, which will be conducted virtually (eg, by telephone or video contact) on Days 42 and 56.

An independent data and safety monitoring board (DSMB) will actively monitor interim data to make recommendations regarding study conduct/continuation. The DSMB will meet once the first 30 subjects complete the Day 7 assessment to perform the first interim analysis of the safety data. Enrollment of 30 additional subjects will proceed if the safety profile of RBT-9 is deemed acceptable (as determined by the DSMB). Two additional DSMB safety and efficacy (futility) analyses will be performed once 60 and 90 subjects complete the Day 7 evaluation. The last DSMB analysis will assess both safety and efficacy (futility) once 150 subjects complete the Day 28 evaluation; sample size re-estimation will also be performed to allow a sample size increase to 252 subjects based on pre-defined conditional power rules.

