#### **9.3.1 Stopping Rules**

For the second, third, and fourth interim analysis, the primary endpoint will be assessed for futility by the DSMB. Enrollment will be stopped if the conditional power is  $<10\%$  based on the percentage of subjects classified in categories 4 through 8 on the 8-point WHO Ordinal Clinical Scale for RBT-9 versus placebo.

Efficacy will be declared at the fourth interim analysis if the conditional power is  $>80\%$  (with all subjects followed through Day 28). If efficacy is declared, the DSMB will advise regarding study continuation.

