#### **11.1 Endpoints**

The following efficacy endpoints are defined for the study.

Primary Endpoint: Percentage of subjects in each treatment group in categories 4 through 8 of the 8-point WHO Ordinal Clinical Scale through Day 28.

Secondary Endpoints:

- Time to first occurrence of either death from any cause or new/worsened organ dysfunction through Day 28, defined as at least one of the following:
  - Respiratory decompensation
  - New or worsening congestive heart failure
  - Requirement of vasopressor therapy and/or inotropic or mechanical circulatory support
  - Ventricular tachycardia or fibrillation lasting at least 30 seconds and/or associated with hemodynamic instability or pulseless electrical activity, or resuscitated cardiac arrest

- Initiation of renal replacement therapy.
- Percentage of subjects who are alive at Day 28.
- Among subjects who begin oxygen therapy, mean change from initiation to last day on oxygen or Day 28 (whichever happens first) in SpO2/FiO2 ratio.
- Percentage of subjects with fever through Day 28.
- Percentage of subjects who develop AKI, as determined by the Investigator, through Day 28.
- Percentage of subjects with new or worsening congestive HF through Day 28.
- Percentage of subjects with ventricular tachycardia or fibrillation lasting at least 30 seconds and/or associated with hemodynamic instability or pulseless electrical activity, or resuscitated cardiac arrest through Day 28.
- Percentage of subjects who remain hospitalized at Day 28.
- Length of hospitalization through Day 28.
- Number of oxygen-free days through Day 28.
- Percentage of subjects transferred to the ICU through Day 28.
- Number of days on mechanical ventilation through Day 28.
- Time to and duration of vasopressor or inotrope utilization through Day 28.
- Percentage of subjects who begin dialysis through Day 28.

Exploratory Endpoints:

- Duration of COVID-19 symptoms through Day 56

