## 11.7 Interim Analysis

A group sequential design will be conducted with 3 pre-planned interim analyses after 30, 60, and 90 subjects complete the Day 7 evaluation and once 150 subjects complete the Day 28 evaluation. At each interim, the DSMB will evaluate an independently conducted analysis in order to assess safety and futility.

The interim analyses will be subject to adaptations according to Cui; 2-sided 0.1% alpha at the second interim and 2-sided 0.2% alpha at each of the third and fourth interim analyses. Enrollment will be stopped if the conditional power is <10% based on the percentage of subjects classified in categories 4 through 8 on the 8-point WHO Ordinal Clinical Scale for RBT-9 versus placebo.

For the second, third, and fourth interim analyses, the conditional power will be assessed. Futility will be declared if the conditional power is <10%, while efficacy will be declared at the fourth interim analysis if the conditional power is >80% (with all subjects followed through Day 28); sample size re-estimation will be performed to increase the sample size to 252 subjects. Enrollment will be recommended if futility is observed. If efficacy is declared, the DSMB will advise regarding study continuation.

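### Interims 2 and 3 apply a conditional-power stop to a through-Day-28 endpoint when only Day 7 follow-up is guaranteed, the calculation is not defined, and the 84-85% power allows for no futility stopping

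*Combined protocol and SAP*

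**What the plan says.** Section 11.1 defines the primary endpoint as "Percentage of subjects in each treatment group in categories 4 through 8 of the 8-point WHO Ordinal Clinical Scale through Day 28".

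The second and third interims are triggered by Day 7 completion. Section 9.3 says "Two additional DSMB interim analyses will be performed once 60 and 90 subjects complete the Day 7 evaluation", and the Synopsis calls these same looks safety and futility analyses: "Two additional DSMB safety and efficacy (futility) analyses will be performed once 60 and 90 subjects complete the Day 7 evaluation". Section 9.3.1 names the endpoint: "For the second, third, and fourth interim analysis, the primary endpoint will be assessed for futility by the DSMB". Section 11.7 gives the rule: "Enrollment will be stopped if the conditional power is <10% based on the percentage of subjects classified in categories 4 through 8".

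Only the fourth interim, at 150 subjects, is tied to Day 28 completion. The full-follow-up condition belongs to its efficacy rule: "efficacy will be declared at the fourth interim analysis if the conditional power is >80% (with all subjects followed through Day 28". The Day 7-triggered looks also carry alpha: "2-sided 0.1% alpha at the second interim and 2-sided 0.2% alpha at each of the third and fourth interim analyses".

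Section 9.3 refers to conditional-power rules set in advance, but the documents give only the cut-offs of 10% and 80%. They do not state the effect assumed for subjects still to come. The target sample size is also unclear: Sections 9.3 and 11.7 treat 252 as the size after an increase, without naming the size before it, while Section 11.6 computes power at 252. Section 11.3 rules out imputation of missing data and does not mention subjects whose Day 28 outcome is still pending. Section 11.6 says the final alpha of 4.5% allows for the interims; it does not mention power lost to futility stops.

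**The concern.** At 60 and 90 subjects the rule projects a Day 28 result from data in which the most recent subjects may have three weeks still to run. On either reading of the endpoint, Day 7 data are not the endpoint. If it means ever in categories 4 to 8 through Day 28, later failures are not yet visible. If it means status at Day 28, Day 7 status is a different quantity and can change in both directions.

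At stake is an early stop of a drug that works as well as the design assumes, at a rate that depends on choices the plan leaves open. The power table would not show it, because it describes a trial that always runs to 252. A DSMB statistician following the text would have to choose the outcome definition, the assumed effect and the target N, possibly after seeing data.

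**Working it through.** **Inputs from the documents.** N = 252 (84 placebo, 168 RBT-9), final two-sided alpha 0.045, failure rates 25% v 10%, 32% v 15% and 38% v 20% (Section 11.6); 2:1 allocation, looks at 60, 90 and 150 (Section 9.3); stop if conditional power is below 10% (Section 11.7).

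**Assumptions, not in the documents.** Conditional power targets the final test at N = 252. The effect for future subjects is either the current trend or the design effect. A stated share of Day 28 failures is visible at looks 2 and 3, the same in both arms unless noted, and the rest are scored as non-failures. Look 4 uses complete data. Early efficacy stops are ignored.

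**Step 1: the plan's own figure.** Power = Φ[(π1 − π2 − 2.005 × SE0)/SE1], with SE0 pooled and SE1 unpooled. For 25% v 10%:
- pooled rate = (84 × 0.25 + 168 × 0.10)/252 = 0.15
- SE0 = √[0.15 × 0.85 × (1/84 + 1/168)] = 0.0477
- SE1 = √[0.25 × 0.75/84 + 0.10 × 0.90/168] = 0.0526
- power = Φ[(0.15 − 2.005 × 0.0477)/0.0526] = Φ(1.033) = 84.9%

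The three scenarios give 84.9%, 85.6% and 84.6% against the stated 84, 85 and 84. The exact chi-square power is 85.7%, 86.0% and 84.9%. The alpha adds up: 0.1 + 0.2 + 0.2 + 4.5 = 5.0%. The stated power therefore reproduces as a fixed-sample figure without futility stops.

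**Step 2: what the 10% rule means.** With t = n/252 and interim statistic Z, CP = Φ[(Z√t + θ(1 − t) − 2.005)/√(1 − t)]. Current trend sets θ = Z/√t; the design effect sets θ = 0.15/0.0477 = 3.14 for 25% v 10%. At n = 60, t = 0.238 and √t = 0.488. CP is below 10% when:
- current trend: Z < 0.488 × (2.005 − 1.282 × √0.762) = 0.43
- design effect: Z < (2.005 − 1.119 − 3.14 × 0.762)/0.488 = −3.09

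Under the design alternative with complete data, Z at 60 subjects has mean 3.14 × 0.488 = 1.53. The chance of a wrongful stop at that look is roughly Φ(0.43 − 1.53) = Φ(−1.10), about 14%, under current trend, and practically zero under the design effect.

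**Step 3: simulated power.** 400,000 trials per case, futility at 60, 90 and 150:

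| Conditional power | Share of failures visible at 60 and 90 | Power: 25v10 / 32v15 / 38v20 | Wrongful stop at 60 |
|---|---|---|---|
| No futility rule | – | 85.7 / 86.0 / 84.9% | – |
| Current trend | 100% | 73.6 / 74.1 / 72.4% | 14-16% |
| Current trend | 70% | 64.4 / 65.2 / 63.8% | 22-23% |
| Current trend | 50% | 57.1 / 56.6 / 55.3% | 29-30% |
| Design effect | 100%, 70% or 50% | at most about 0.2 points lost | about 0% |

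**Step 4: splitting the loss for 25% v 10% under current trend.** The looks themselves, with complete data, cost 85.7 − 73.6 = 12.1 points. Incomplete outcomes add 73.6 − 64.4 = 9.2 points at 70% visible, or 73.6 − 57.1 = 16.5 at 50%. Most of the 12.1 comes from the small looks: futility at 150 alone leaves 83.4 / 83.7 / 82.5%.

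**Step 5: unequal visibility.** With futility at 60 and 90 only, and 75% of placebo but all RBT-9 failures visible, current-trend power is 57.0 / 54.5 / 49.2%. Under the design effect the worst case run (50% of placebo and 75% of RBT-9 failures visible, 38% v 20%) gives 84.2% against 84.9% without futility, a loss of about 0.8 points.

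**The case against.** The strongest reply is that the loss depends on an input the plan leaves open. If conditional power is computed at the design effect, almost nothing is lost whatever share of failures is visible. Section 11 defers full detail to a separate analysis plan, which may settle this. That stands. A reader might infer that the stated power is not delivered, and the documents do not support that: the result runs from almost no loss to about 30 points according to an unstated choice.

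Three further inferences are tempting and also go too far.
- That subjects at looks 2 and 3 have been followed only to Day 7. Day 7 is the minimum. Earlier enrollees may have reached Day 28, and no accrual rate is given, so a single visible share is a simplification.
- That later failures are counted as successes. No section says so. The no-imputation rule could equally mean that subjects without Day 28 status are left out. The 70% and 50% rows rest on the first handling.
- That Day 7 data cause the whole loss. Under current trend, complete Day 28 data still give only about 72-74%.

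The visible shares are also open. If the endpoint means ever in categories 4 to 8, failures may come early, since subjects may enter on supplemental oxygen and the scale is scored from Day 1. If it means status at Day 28, the shares do not apply.

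None of this removes the mismatch. The protocol itself fixes the trigger, the endpoint and the stop, and leaves undefined the quantities that decide whether the rule is harmless.

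**Conclusion.** The concern holds as a mismatch with an undefined calculation. A binding-sounding stop is applied to a through-Day-28 endpoint at looks where only Day 7 follow-up is assured, and the 84-85% power is a fixed-sample figure that may not be delivered. Relative to about 85-86% without futility, the loss is about 12 points under current-trend conditional power with complete data, and about 21 to 30 points if 70% or 50% of failures are visible and the rest are scored as non-failures. Under the design effect it is at most about 0.2 points at these shares. These sizes assume N = 252 as the target, the design failure rates and the stated shares; event timing and accrual are not in the documents. The inconsistency between trigger and endpoint needs none of these assumptions.

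**What to change.** 1. Keep the Day 7 trigger at 60 and 90 subjects for safety review.
2. Base futility at those looks on subjects with complete Day 28 status, or on a model, stated in advance, that predicts Day 28 status from earlier data. Say whether the endpoint means ever through Day 28 or status at Day 28.
3. State that conditional power targets N = 252 and is computed under the design alternative, naming which of the three scenarios applies. Step 2 alone is not enough: under current trend, complete Day 28 data do not restore 84-85%.
4. Restate power in the Synopsis and Section 11.6 with the futility rule applied.
5. Say which data any test using the 0.1% and 0.2% alpha at these looks would use. Reconcile the sentence in Section 11.7 and the Synopsis that recommends enrollment when futility is seen with the sentence that stops it.

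The cost is wording in the protocol and DSMB charter. The futility part of looks 2 and 3 comes about three weeks later (28 − 7 = 21 days) or rests on fewer subjects. Design-effect futility will also rarely stop early: at 60 subjects it needs Z below about −3.1, which even a drug with no effect would reach about 0.1% of the time. The sponsor should accept that knowingly; if earlier stopping is wanted, its power cost belongs in the power table.
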